11.3 Site monitoring

Before study initiation, at a site initiation visit or at an investigator's meeting, Novartis personnel (or designated CRO) will review the protocol and eCRFs with the investigators and their staff. During the study, the field monitor will visit the site regularly to check the completeness of patient records, the accuracy of entries on the eCRFs, the adherence to the protocol to Good Clinical Practice, the progress of enrollment, and to ensure that study treatment is being stored, dispensed, and accounted for according to specifications. Key study personnel must be available to assist the field monitor during these visits.

The investigator must maintain source documents for each patient in the study, consisting of case and visit notes (hospital or clinic medical records) containing demographic and medical information, laboratory data, electrocardiograms, and the results of any other tests or assessments. All information recorded on eCRFs must be traceable to source documents in the patient's file. The investigator must also keep the original signed informed consent form (a signed copy is given to the patient).

The investigator must give the monitor access to all relevant source documents to confirm their consistency with the eCRF entries. Novartis monitoring standards require full verification for the presence of informed consent, adherence to the inclusion/exclusion criteria and documentation of SAEs. Additional checks of the consistency of the source data with the eCRFs are performed according to the study-specific monitoring plan.

11.4 Data Confidentiality

Information about study subjects will be kept confidential and managed under the applicable laws and regulations. Those regulations require a signed subject authorization informing the subject of the following:

1. What protected health information (PHI) will be collected from subjects in this study?
2. Who will have access to that information and why?
3. Who will use or disclose that information?
4. The rights of a research subject to revoke their authorization for use of their PHI.

In the event that a subject revokes authorization to collect or use PHI, the investigator, by regulation, retains the ability to use all information collected prior to the revocation of subject authorization. For subjects that have revoked authorization to collect or use PHI, attempts should be made to obtain permission to collect follow-up safety information (e.g. has the subject experienced any new or worsened AEs) at the end of their scheduled study period.

The data collection system for this study uses built-in security features to encrypt all data for transmission in both directions, preventing unauthorized access to confidential patient information. Access to the system will be controlled by a sequence of individually assigned user identification codes and passwords, made available only to authorized personnel who have completed prerequisite training.

12 Data analysis and statistical methods

The final analysis will be conducted and the clinical study report (CSR) written once all patients have completed the study (i.e. completed the long-term follow-up period of Month 24) or discontinued earlier. Analysis cut-off date will be defined corresponding to the analysis time point and all data captured in the study up to that cut-off will be reported. Any data analysis carried out independently by the investigator should be submitted to Novartis before publication or presentation.

12.1 Analysis sets

If the starting dose is different from the assigned dose level due to co-administration of ruxolitinib with strong CYP3A4 inhibitors or dual CYP3A4/CYP2C9 inhibitors, these patients will be included under the assigned dose level and considered that they have received the full assigned dose. This applies to Full Analysis Set, Safety Set and Efficacy Evaluable Set as described below.

The **Full Analysis Set (FAS)** comprises all patients to whom study treatment has been assigned and who received at least one dose of study treatment. Patients will be analyzed according to the treatment they have been assigned to.

The **Safety Set** includes all patients who received at least one dose of study treatment. Patients will be analyzed according to the study treatment received, where treatment received is defined as the assigned dose level of ruxolitinib if the patient took at least one dose of that treatment or the first dose level received if the assigned dose level was never received.

The **Pharmacokinetic Analysis Set (PAS)** includes all patients who provide at least one evaluable PK concentration. For a concentration to be evaluable, patients are required to:

1. Take the dose of ruxolitinib prior to PK sample.
2. For pre-dose samples, do not vomit within 2 hours after the dosing of ruxolitinib prior to sampling; for post-dose samples, do not vomit within 2 hours after the dosing of ruxolitinib.

The PAS will be used for Non-compartmental analysis (NCA) for patients where extensive PK sampling is obtained. This analysis set will also be used for any exposure-response analysis

The **Efficacy Evaluable Set** (EES) comprises all patients to whom study treatment has been assigned at the Recommended Phase 2 dose (RP2D) of ruxolitinib and who received at least one dose of study treatment at that dose level. If the starting dose is different from the RP2D due to co-administration of ruxolitinib with strong CYP3A4 inhibitors or dual CYP3A4/CYP2C9 inhibitors, these patients will be included in the EES.

12.2 Subject demographics and other baseline characteristics

Baseline is the last non-missing assessment or procedure conducted prior to or on the treatment start date.

Demographic and other baseline data including disease characteristics will be listed and summarized descriptively by group for the FAS.

Categorical data will be presented as frequencies and percentages. For continuous data, mean, standard deviation, median, minimum, and maximum will be presented.

Relevant medical histories and current medical conditions at baseline will be summarized by system organ class and preferred term, by group.

The groups are defined in [Table 3-1](#) and [Table 3-2](#). If the Phase I preliminary dose is different to RP2D, baseline characteristic data will be listed and summarized by age group and dose level.

12.3 Treatments

The Safety set will be used for the analyses below. Categorical data will be summarized as frequencies and percentages. For continuous data, mean, standard deviation, median, 25th and 75th percentiles, minimum, and maximum will be presented.

The duration of exposure in days to ruxolitinib will be summarized by means of descriptive statistics. The dose intensity (computed as the ratio of actual cumulative dose received and actual duration of exposure) for the ruxolitinib arm will be summarized.

The number of patients with dose adjustments and the reasons will be summarized by group and all dosing data will be listed.

Concomitant medications and significant non-drug therapies prior to and after the start of the study treatment will be listed and summarized according to the Anatomical Therapeutic Chemical (ATC) classification system by group.

If the Phase I preliminary dose is different to RP2D, treatment data will be listed and summarized by age group and dose level.

12.4 Analysis of the primary endpoint(s)

The primary objective of the Phase I is to assess pharmacokinetic (PK) parameters of ruxolitinib for patients with aGvHD and SR-aGvHD and define an age appropriate RP2D for each of the groups 2-4. The primary objective of the Phase II is to measure the activity of ruxolitinib in patients with aGvHD or SR-aGvHD assessed by Overall Response Rate (ORR) at Day 28.

12.4.1 Definition of primary endpoint(s)

The primary endpoint of the Phase I is the list of following PK parameters (AUC, Cmax, T1/2, Ctrough, and other parameters, as appropriate) which will be derived using non-compartmental methods in subjects with extensive sampling (Groups 1, 2, and 3). These parameters will then be used to define a RP2D for Groups 2, 3, and 4. The observed PK parameters (within group) will be summarized and compared to information obtained from adult and adolescent aGvHD patients treated with ruxolitinib on study [\[CINC424C2301\]](#). Data from patients older than 2 years old will be combined and analyzed by PBPK methods to determine the dose to be administered in patients younger than 2 years old (Group 4).

The primary endpoint for the Phase II is the overall response rate (ORR) at Day 28, defined as the proportion of patients with complete response (CR) or partial response (PR) without requirement for additional systemic therapies for an earlier progression, mixed response or non-response as per [Table 8-3 \(Harris et al 2016\)](#). Note that response is relative to the assessment of aGvHD at the start of study treatment.

- **Complete-response** is defined as a score of 0 for the aGvHD grading in all evaluable organs that indicates complete resolution of all signs and symptoms of aGvHD in all evaluable organs without administration of additional systemic therapies for any earlier progression, mixed response or non-response of aGvHD.
- **Partial response** is defined as improvement of 1 stage in 1 or more organs involved with aGvHD signs or symptoms without progression in other organs or sites without administration of additional systemic therapies for an earlier progression, mixed response or non-response of aGvHD.
- **Lack of response** is defined as no response, mixed response, or progression.
- **No response** is defined as absence of improvement in any organ involved by aGvHD, without worsening in any involved organ.
- **Mixed response** is defined as improvement of at least 1 stage in the severity of aGvHD in at least one organ accompanied by progression in another organ or development of signs or symptoms of aGvHD in a new organ.
- **Progression** is defined as worsening in 1 or more organs by 1 or more stages without improvement in any involved organ

Patients requiring additional systemic therapy for aGvHD will be classified as non-responders, and patients with missing baseline or Day 28 aGvHD response assessment will be considered as treatment non-responders.

aGvHD Flare is defined as any increase in signs or symptoms of aGvHD that is sustained for >24h after an initial response (CR or PR) and requires re-escalation of immunosuppressive therapy (e.g. corticosteroid, CNI and/or ruxolitinib dosing). While all aGvHD flares will be captured on study whether occurring during steroid, CNI or ruxolitinib taper. Only flares in GvHD that require new additional systemic therapy, will be considered aGvHD flare failure.

Acute GvHD will be assessed as per [Table 8-2 \(Harris et al 2016\)](#). Grade will be calculated based on the staging of the organs and recorded on the eCRF by the Investigator. The Investigator reported grade will be used for all analyses. Grade and response will be calculated by the sponsor for the purposes of data review and sensitivity analysis.

12.4.2 Statistical model, hypothesis, and method of analysis

Pharmacokinetic parameters for patients in Groups 1, 2, 3 and 4 (who are part of the PAS) will be compared to adult information from study [\[\[CINC424C2301\]\]](#) through the use of ANOVA methods. The geometric mean ratio with 90% CI will be provided.

The response rates for ORR at Day 28 will be estimated on the Efficacy Evaluable Set (EES). 90% confidence intervals will be calculated based on the exact method for binomial distribution. Summary statistics (frequencies and percentages) will be provided.

12.4.3 Handling of missing values/censoring/discontinuations

Patients with missing assessments that prevent the evaluation of the ORR will be considered non-responders. This includes aGvHD response assessments at baseline and Days 28, 56. Patients who discontinue the study treatment prior to the completion of the Day 28 visit will be considered non-responders.

The following analysis windows will be applied to the target day for assessments on overall response, where target day for Week X is X*7.

Baseline assessment is the last aGvHD assessment prior to or at the start of study treatment (Day 1).

Weeks 1, 2, 3, 4, 5, 6, 7, 8: -3 days/+3 days

Weeks 12 to 48: -13 days/+14 days

12.4.4 Sensitivity and Supportive analyses

As supportive analyses, the estimate of response rates ORR at Day 28 will be presented by diagnosis (treatment naïve aGvHD and SR-aGvHD) on the EES.

12.5 Analysis of secondary endpoints

12.5.1 Efficacy and/or Pharmacodynamic endpoint(s)

The main secondary objective of the study is to estimate the proportions of all patients who achieve a complete response (CR) or partial response (PR) at Day 28 and maintain a CR or PR at Day 56. A patient will not be considered a durable responder at Day 56 if any of the following events occurs prior to or at Day 56:

- No CR or PR at Day 28 or at Day 56.
- aGvHD progression or additional systemic therapy for aGvHD

The durable response rates for ORR at Day 56 will be estimated with 90% confidence intervals on EES. Summary statistics (frequencies and percentages). The confidence intervals will be calculated based on the exact method for binomial distribution.

All secondary efficacy endpoint analyses will be analyzed using the EES.

- Overall Response Rate at Day 14, will be derived in the same way as the primary variable ORR at Day 28.
- Duration of response (DOR)

Duration of response will be calculated for patients whose overall response at Day 28 is CR or PR according to updated standard criteria ([Harris et al 2016](#)). The start date is the date of first documented response of CR or PR (i.e., the start date of response), and the end date is defined as the date of progression or the date of addition of systemic therapies for aGvHD, since this constitutes a non-response.

Death without prior observation of aGvHD progression and onset of chronic GvHD are considered to be competing risks.

Duration of response will be censored at the last response assessment prior to or at the analysis cut-off date, if no events/competing risk occurred before or at of cut-off date.

DOR will be listed and summarized for all patients on the EES with overall response of CR or PR at Day 28.

- Overall survival (OS)

Overall survival is defined as the time from date of the start of study treatment to date of death due to any cause. If a patient is not known to have died, then OS will be censored at the latest date the patient was known to be alive (on or before the cut-off date).

The OS distribution will be estimated using the Kaplan-Meier method, and the Kaplan-Meier curves, medians, 1, 2, 6, 12, 18 and 24 month survival estimates and 95% confidence intervals will be presented.

- Event Free Survival (EFS)

Event-free survival is defined as the time from the study treatment start date to the date of hematologic disease relapse/progression, graft failure or death due to any cause. If a patient is not known to have any event, then EFS will be censored at the latest date the patient was known to be alive (on or before the cut-off date). The EFS distribution will be estimated using the Kaplan-Meier method, and the Kaplan-Meier curves, medians, 1, 2, 6, 12, 18 and 24 month survival estimates and 95% confidence intervals will be presented.

- Failure Free Survival (FFS)

Failure-free survival is defined as the time from the study treatment start date to date of hematologic disease relapse/progression, non-relapse mortality or addition of new systemic aGvHD treatment.

Cumulative incidence of FFS at 1, 2, 6, 12, 18 and 24 months will be estimated, considering each event as a competing risk for the other two. Onset of chronic GvHD is considered as a competing risk for all three types of failure.

- Non-relapse mortality (NRM)

Non-relapse mortality is defined as the time from the study treatment start date to date of death not preceded by hematologic disease relapse/progression. Hematologic disease relapse/progression is considered a competing risk for NRM with the date of hematologic disease relapse/progression being the earlier of documented hematologic disease relapse/progression or institution of therapy to treat potential hematologic disease relapse/progression. If a patient is not known to have died or to have relapsed/progressed, then NRM will be censored at the latest date the patient was known to be alive (on or before the cut-off date).

NRM will be analyzed on the EES for all patients. The cumulative incidence curve for NRM as well as estimates at 1, 2, 6, 12, 18 and 24 months with 95% confidence intervals will be presented.

- Incidence of Malignancy Relapse/Progression (MR)

Malignancy relapse/progression is defined as the time from the study treatment start date to date of hematologic malignancy relapse/progression. Deaths not preceded by hematologic malignancy relapse/progression are competing risks. If a patient is not known to have event or competing risks, then MR will be censored at the latest date the patient was known to be alive (on or before the cut-off date). The cumulative incidence of MR will be estimated for patients with underlying hematologic malignant disease, accounting for NRM as the competing risk.

In addition, the proportion of patients who had hematologic malignancy relapse/progression and its 95% confidence interval will be presented for patients with underlying hematologic malignant disease.

- Best Overall Response (BOR)

Best overall response rate, is defined as the proportion of patients with complete response (CR) or partial response (PR) at any time point (up to and including Day 28 and before the start of additional systemic therapy for aGvHD).

- Cumulative steroid dosing until Day 56

Overall and weekly cumulative steroid dose for each patient up to Day 56 will be tabulated.

- Incidence of cGvHD

cGvHD is defined as the diagnosis of any cGvHD including mild, moderate, severe. Incidence of cGvHD is the time from the start of treatment to onset of cGvHD. Cumulative incidence of cGvHD will be estimated, accounting for deaths without prior onset of cGvHD and hematologic disease relapse/progression as the competing risks. If a patient is not known to have event or competing risks, then the incidence of cGvHD will be censored at the latest date the patient was known to be alive (on or before the cut-off date).

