6.1.5.1 Tapering Guidelines

Tapering of immunosuppression will follow 2 steps: first taper of corticosteroids, followed with taper of CNI and/or ruxolitinib in responding patients. If applicable, the taper of CNI and ruxolitinib may be performed at the same time.

During the Treatment Period, immunosuppression taper guidelines are:

1. **Corticosteroids:** the taper of corticosteroids in patients demonstrating a PR or CR as observed by the Investigator must not be initiated earlier than Day 7, and should then be performed per institutional guidelines (e.g. 10% dose reduction every 5 days, beginning no earlier than Day 7 and continuing to approximately Day 56 to allow 7-8 week taper).
2. **CNI (cyclosporine or tacrolimus):** CNI taper is allowed in patients demonstrating a PR or CR, once off corticosteroids, and should then be performed per institutional guidelines (e.g. 25% dose reduction per month).
3. **Ruxolitinib:** ruxolitinib taper is allowed in patients demonstrating a PR or CR, once off corticosteroids, and must not start earlier than Day 56.

The following guidance may be followed based on evaluation of the condition of the patient, current dosing regimen and the clinical judgment of the Investigator: a 50% dose reduction every 2 months (approximately every 56 days), i.e., initial dose reduction from 10 mg BID to 5 mg BID and, if sustained aGvHD stable disease is observed, patient is further tapered by a second 50% dosage reduction to 5 mg QD for an additional 56 days, prior to cessation. No further reductions will be allowed beyond once a day dose. Refer to [Table 6-4](#).

It is expected that the taper of corticosteroids, CNI, and ruxolitinib will be completed by the end of Week 24. Should an aGvHD flare or other safety concern prevent taper from being complete by then, the dose of ruxolitinib may be maintained until Week 24. Ruxolitinib taper completion will be consequently delayed beyond Week 24, but must be complete by Week 48 maximum.

All patients **must** be off corticosteroids, CNIs and ruxolitinib by the Week 48 maximum.

6.1.5.1.1 aGvHD flare

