3.4.2.4 Systemic corticosteroid during study treatment

Doses of methylprednisolone will be converted to prednisone equivalents by multiplying the methylprednisolone dose by 1.25 and will be reported in mg/kg/day

The duration of exposure will be summarized for systemic corticosteroid by age group. It will also be categorized into time intervals; frequency counts and percentages will be presented for the number (%) of patients in each interval. The actual cumulative dose, dose intensity and

relative dose intensity (relative to the starting dose of corticosteroids) will be summarized up to Day 28, Day 56 and end of on-treatment period.(Section 3.4.1) This analysis will be based on Safety Set. The data will be reported on the Study treatment eCRF through the end of treatment period per EOT Disposition eCRF, and on the Prior and Concomitant Medications eCRF for any data prior and after the end of treatment. The list of systemic corticosteroids will be documented in Data Quality Plan.

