Event-free survival is defined as the time from the study treatment start date to the date of hematologic disease relapse/progression, graft failure or death due to any cause. If a patient is not known to have any event, then EFS will be censored at the latest date the patient was known to be alive (last contact date on or before the cut-off date).

- **Failure Free Survival (FFS)**

Failure-free survival is defined as the time from the study treatment start date to date of hematologic disease relapse/progression, non-relapse mortality (NRM) or addition of new systemic aGvHD treatment. Each type of failure as a competing risk for the other two, and onset of chronic GvHD is considered as a competing risk for all three types of failure. If a patient is not known to have any event or competing risk, then FFS will be censored at the latest date the patient was known to be alive (last contact date on or before the cut-off date).

- **Non-relapse mortality (NRM)**

Non-relapse mortality is defined as the time from the study treatment start date to date of death not preceded by hematologic disease relapse/progression. Hematologic disease relapse/progression is considered a competing risk for NRM with the date of hematologic disease relapse/progression being the earlier of documented hematologic disease relapse/progression or institution of therapy to treat potential hematologic disease relapse/progression. If a patient is not known to have died or to have relapsed/progressed, then NRM will be censored at the latest date the patient was known to be alive (last contact date on or before the cut-off date).

- **Incidence of Malignancy Relapse/Progression (MR)**

Malignancy relapse/progression is defined as the time from the study treatment start date to date of hematologic malignancy relapse/progression. Deaths not preceded by hematologic

malignancy relapse/progression are competing risks. If a patient is not known to have event or competing risks, then MR will be censored at the latest date the patient was known to be alive (last contact date on or before the cut-off date).

- **Cumulative steroid dosing until Day 56**

The weekly cumulative steroid dose will be calculated for each patient up to Day 56 and the overall cumulative steroid dose will be calculated for each patient at Day 56. In addition, the proportion of patients with any dose reduction and any dose reduction of at least 50% in corticosteroids from baseline until EOT will be provided.

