The cumulative incidence curve for MR and estimates at 1, 2, 6, 12, 18 and 24 months with 95% confidence intervals will be presented for patients with underlying hematologic malignant disease, accounting for NRM as the competing risk.

- **Cumulative steroid dosing until Day 56**

Overall and weekly cumulative steroid dose for each patient up to Day 56 or discontinuation of study treatment will be tabulated. In addition, the relative dose intensity (RDI), by week, will be calculated relative to the starting dose of corticosteroids and categorized as (1) complete reduction where patients are tapered off corticosteroids by D56, (2) $\leq 50\%$ RDI and (3) $> 50\%$ RDI. The proportion of patients in each category and corresponding 95% confidence intervals will be presented.

- **Incidence of cGvHD**

The cumulative incidence of cGvHD and estimates at 1, 2, 6, 12, 18 and 24 months with 95% confidence intervals will be presented, accounting for deaths without prior onset of cGvHD and hematologic disease relapse/progression as the competing risks. The cumulative incidence curve will be plotted.

- **Graft failure**

Summary statistics of graft failure assessment will be presented over time and at any timepoint by dose level and for all patients. In case of very few patients with graft failure (e.g. less than 5 patients), descriptions using only listings will be provided instead.

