3.7.3 Handling of missing values/censoring/discontinuations

Patients with missing assessments that prevent the evaluation of the ORR at Day 14 will be considered non-responders. This includes missing aGvHD assessments at baseline and/or Day 14. The time window for the Day 14 visit is defined in [Section 2.5.3](#).

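### Cumulative steroid dose to Day 56 ignores time alive, so early death on unreduced steroids lowers the total and the summary can read as steroid sparing

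*Protocol*

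**What the plan says.** Protocol 12.5.1 defines the analysis in one sentence: "Overall and weekly cumulative steroid dose for each patient up to Day 56 will be tabulated". SAP 3.7.1 adds that "the overall cumulative steroid dose will be calculated for each patient at Day 56". SAP 3.7.2 gives a slightly different end point: "Overall and weekly cumulative steroid dose for each patient up to Day 56 or discontinuation of study treatment will be tabulated".

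SAP 3.7.2 also plans a relative measure: "the relative dose intensity (RDI), by week, will be calculated relative to the starting dose of corticosteroids". It has three categories with 95% confidence intervals. The first is "complete reduction where patients are tapered off corticosteroids by D56"; the others are relative dose intensity (RDI) of 50% or less and of more than 50%. There is no category for death.

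SAP 3.7.3, on missing values for the secondary endpoints, covers only Day 14 response: "Patients with missing assessments that prevent the evaluation of the ORR at Day 14 will be considered non-responders". It does not mention steroid dose.

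Three other provisions bear on the point:

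- SAP 3.4.2.4 (Safety Set), besides cumulative dose and dose intensity for steroids: "relative dose intensity (relative to the starting dose of corticosteroids) will be summarized up to Day 28, Day 56 and end of on-treatment period".
- SAP 3.7.1: the proportions of patients with any steroid reduction, and with a reduction of at least 50%, from baseline to end of treatment.
- SAP 3.1: a missing category where applicable, with percentages based on the relevant population.

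**The concern.** A raw sum over a fixed window measures dose only if everyone can contribute for the whole window. Death shortens the contribution, and the sum then falls for a reason that has nothing to do with tapering. The error has a direction: the worst outcome pulls the total the same way as success.

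The plan deals with death elsewhere. It is a competing risk for duration of response, malignancy relapse, chronic GvHD and grade 3 infection, and a missing Day 56 assessment rules out durable response. So at the same Day 56 horizon, a child who dies on Day 20 fails the key secondary endpoint but lowers the steroid total.

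Steroid sparing is among the clinical benefits that Protocol 1.2 expects, and cumulative steroid dose to Day 56 is a named secondary objective in Protocol Table 2-1. A low mean total is likely to be read as evidence for that benefit.

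**Working it through.** **Plan's own figure.** The documents give none for the steroid endpoint, so there is nothing to reproduce. The efficacy sizing figure (0.901 for 45 patients) concerns Day 28 response and does not bear on this point.

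**Inputs**

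- Example taper, Protocol 6.1.5.1: "10% dose reduction every 5 days, beginning no earlier than Day 7 and continuing to approximately Day 56".
- Starting dose: 2 mg/kg/day prednisone equivalent. This is an assumption; Protocol 6.2.1.1 gives it only as a cap for patients over 100 kg. The break-even days do not depend on it.
- 45 patients (Protocol 12.8.1).
- Survival figures quoted in Protocol 1.1.2.1.2: 79% at 6 months (retrospective survey), median 11.1 months (ruxolitinib arm of the randomised phase III trial), 51.0% at 6 months (single-arm phase II trial).

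**Step 1. Total for a survivor who completes the taper**, in multiples of the starting daily dose. Days 1 to 6 are at full dose, then 5-day steps follow.

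- Each step 10% of the starting dose: 6 + 5 × (0.9 + 0.8 + … + 0.1) = 6 + 22.5 = 28.5, or 57 mg/kg.
- Each step 10% of the current dose: 6 + 5 × (sum of 0.9^k, k = 1 to 10) = 35.3, or 70.6 mg/kg.

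**Step 2. Total for a child on unreduced dose who dies on Day D.** The total is D. It lies below 28.5 for any death up to Day 28, and below 35.3 for any death up to Day 35. For death on Day 20: 20 × 2 = 40 mg/kg against 57, which is 1 − 40/57 = 30% lower. Dose per day alive is 2.0 mg/kg/day, against 57/56 = 1.02 for the survivor.

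**Step 3. The relative measure depends on an unstated denominator.** Take a death on Day 14 at full dose.

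- Over days on steroids: RDI is 14/14 = 1.00. The survivor scores 28.5/51 = 0.56 or 35.3/56 = 0.63. The ranking is correct.
- Over all 56 days: RDI is 14/56 = 0.25, in the 50%-or-less category. The ranking is wrong.
- By week, as SAP 3.7.2 specifies: weeks after death have no exposure. Scored as zero, they fall at 50% or less from week 3; the survivor on the first taper first gets there in week 5 (0.443). Otherwise they are missing or omitted. The SAP does not say which.

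**Step 4. Size in the study.** With an exponential hazard, expected deaths by Day 56 among 45 patients are:

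- 45 × (1 − 0.79^(56/182.625)) = 3.1
- 45 × (1 − 0.5^((56/30.4375)/11.1)) = 4.9
- 45 × (1 − 0.51^(56/182.625)) = 8.4

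Place k deaths on Day 14 at full dose (28 mg/kg each) and let the others complete the first taper (57 mg/kg each). The mean total is [(45 − k) × 57 + k × 28]/45. The pooled dose per day alive is the same numerator over (45 − k) × 56 + k × 14.

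| Deaths k | Mean total, mg/kg | Change | Dose per day alive, mg/kg/day |
|---|---|---|---|
| 0 | 57.0 | – | 1.02 |
| 3 | 55.1 | −3% | 1.04 |
| 5 | 53.8 | −6% | 1.05 |
| 8 | 51.8 | −9% | 1.07 |

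The two summaries move in opposite directions.

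**The case against.** The strongest reply is that the total does not stand alone, and much of this is right.

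- SAP 3.4.2.4 plans dose intensity and RDI to Day 56, with reference to SAP 3.4.1. There, dose intensity is cumulative dose over duration of exposure (written for ruxolitinib), and steroid duration runs from first to last dose. On that definition the Day 20 death scores 2.0 mg/kg/day and RDI 1.00.
- The SAP 3.7.1 proportions with any, or at least 50%, reduction would show a child who died on full dose as having none.
- Early deaths are not hidden: survival endpoints are estimated at 1 and 2 months, and all deaths are summarised and listed.
- The endpoint is descriptive, in a single-arm study, with no test, threshold or control.

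These points limit the harm but do not repair the endpoint. The dose-intensity table is an exposure summary on the Safety Set, whereas the secondary efficacy endpoints use the Efficacy Evaluable Set. Neither it nor the reduction proportions change the total or say how weeks after death enter the weekly categories. The general missing category in SAP 3.1 may catch those weeks, but would mix deaths with absent records.

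A reader might infer that the plan counts a child who dies early as steroid-sparing. It does not: nothing classifies patients on the total. Nor does the wording of the first weekly category describe a child who died on full dose, since that child was never tapered off. A reader might also turn all expected deaths by Day 56 into a share of patients misclassified. That is unsupported: only deaths on unreduced dose by Day 28 (or 35) fall below the example taper, and no rule assigns them to a favourable category.

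**Conclusion.** The point holds as a gap in a descriptive secondary endpoint. The total to Day 56, or to discontinuation, takes no account of time alive, so early death on unreduced steroids lowers it and the summary can move the wrong way. The break-even days (28 or 35) follow from the example taper alone.

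The 3% to 9% fall in the mean total is illustrative. It rests on the 2 mg/kg/day starting dose (for the mg/kg values, not the percentages), all deaths on Day 14 at full dose, every survivor completing the first taper, and an exponential hazard. The survival figures come from steroid-refractory patients, mainly older than those in this study. Later deaths, or deaths after some reduction, would shift the mean less.

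The primary endpoint, the key secondary endpoint and the survival analyses are unaffected. The different end points in SAP 3.7.1 and 3.7.2 are a separate matter: patients without a response at Day 28 must stop study treatment (Protocol 6.1.5), so SAP 3.7.2 cuts their totals too. Correcting that would not resolve the point about death.

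**What to change.** In SAP 3.7.1 and 3.7.2:

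1. Beside the cumulative total, report mean daily steroid dose per day alive to Day 56, in mg/kg/day prednisone equivalent, labelled as a while-alive measure. State whether it is pooled (total dose over total days alive, as in the table above) or averaged over patients.
2. In the weekly RDI table, show death before Day 56 as its own category, so that it is neither scored as zero dose nor left in a general missing category.

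No new data are needed: steroid dosing and dates of death are already collected. The cost is a few lines of SAP text, one derivation, and one more column and row. The while-alive figure must be read with the survival results, because it does not itself count death as a bad outcome.
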